Appendix 2: Example Clinical Laboratory Test Pediatric Reference Ranges

The central laboratory reference ranges will be used for the clinical laboratory tests required for this study.

Example pediatric reference ranges for clinical laboratory tests are provided in the following tables as a guide (Hughes, 2018). A limitation of the example reference ranges is the small sample sizes of patients in many studies that were used to derive the ranges; therefore, caution should be used in their interpretation. Reference values for clinical laboratory tests vary depending on the analytical method used. Therefore, investigators are to use the age-specific reference ranges from the local laboratory to determine whether a test result is abnormal and clinically significant.

Table 1: Example Blood Chemistry Reference Ranges

Analyte	Conventional Units	International System of Units (SI)
Alanine aminotransferase (ALT)		
1-3 years	5-45 U/L	5-45 U/L
4-6 years	10-25 U/L	10-25 U/L
Alkaline phosphatase		
Infant	150-420 U/L	150-420 U/L
2-10 years	100-320 U/L	100-320 U/L
Aspartate aminotransferase (AST)		
10 days-24 months	9-80 U/L	9-80 U/L
> 24 months		
Female	13-35 U/L	13-35 U/L
Male	15-40 U/L	15-40 U/L
Bilirubin (total)		
Infant (> 5 days) – preterm	< 2 mg/dL	< 34 µmol/L
Infant (> 5 days) – term	< 1.2 mg/dL	< 21 µmol/L
Adult	< 1.5 mg/dL	< 20.5 µmol/L
Bilirubin (conjugated)		
Infants/children	< 0.2 mg/dL	< 3.4 µmol/L
Blood urea nitrogen (BUN)		
Infant/child	5-18 mg/dL	1.8-6.4 mmol/L
Calcium (total)		
10 days-24 months	9.0-11.0 mg/dL	2.25-2.75 mmol/L
24 months-12 years	8.8-10.8 mg/dL	2.2-2.7 mmol/L
Calcium (ionized)		
1-18 years	4.9-5.5 mg/dL	1.22-1.37 mmol/L
Carbon dioxide (PaCO ₂)		
Child/adult	32-48 mmHg	

Analyte	Conventional Units	International System of Units (SI)
Chloride (serum)		
6-12 months	97-106 mEq/L	97-106 mmol/L
Child/adult	97-107 mEq/L	97-107 mmol/L
Cholesterol (total)		
Child/adolescent		
Desirable	< 170 mg/dL	
Borderline	170-199 mg/dL	
High	> 200 mg/dL	
Creatine kinase (creatinine phosphokinase)		
> 6 weeks-adult male	20-200 U/L	20-200 U/L
> 6 weeks-adult female	20-180 U/L	20-180 U/L
Creatinine (serum, enzymatic)		
Infant	0.2-0.4 mg/dL	18-35 µmol/L
Child	0.3-0.7 mg/dL	27-62 µmol/L
Gamma-glutamyl transferase (GGT)		
4 months-10 years	5-32 U/L	5-32 U/L
Glucose (serum)		
Newborn, > 1 day	50-90 mg/dL	2.8-5.0 mmol/L
Child	60-100 mg/dL	3.3-5.5 mmol/L
Lactate dehydrogenase (at 37°C)		
10 days-24 months	180-430 U/L	180-430 U/L
24 months-12 years	110-295 U/L	110-295 U/L
Phosphorus		
10 days-24 months	4-6.5 mg/dL	1.29-2.10 mmol/L
3-9 years	3.2-5.8 mg/dL	1.03-1.87 mmol/L
Potassium		
Infant	4.1-5.3 mEq/L	4.1-5.3 mmol/L
Child	3.4-4.7 mEq/L	3.4-4.7 mmol/L
Proteins (protein electrophoresis)		
Total		
15 days-1 year	5.1-7.3 g/dL	
1-2 years	5.6-7.5 g/dL	
3-16 years	6.0-8.0 g/dL	
Albumin		
15 days-1 year	2.2-4.8 g/dL	
1-2 years	3.6-5.2 g/dL	
3-16 years	3.6-5.2 g/dL	
Sodium		
> 1 year	135-147 mEq/L	135-147 mmol/L

Analyte	Conventional Units	International System of Units (SI)
Triglycerides (total)		
1-3 years male	27-125 mg/dL	0.31-1.41 mmol/L
1-3 years female	27-125 mg/dL	0.31-1.41 mmol/L
4-6 years male	32-116 mg/dL	0.36-1.31 mmol/L
4-6 years female	32-116 mg/dL	0.36-1.31 mmol/L
Uric acid		
1-12 months	1.1-5.6 mg/dL	0.065-0.33 mmol/L
1-5 years	1.7-5.8 mg/dL	0.1-0.35 mmol/L

Source: Adapted from [Hughes, 2018](#).

Table 2: Example Hematology Reference Values

Blood Cell Indices	Age	
	6 Months-2 Years	2-6 Years
Hemoglobin, g/dL [1]	12.0 (10.5)	12.5 (11.5)
Hematocrit, % [1]	36 (33)	37 (34)
Mean corpuscular hemoglobin concentration, g/dL RBC [1]	33.0 (30.0)	34.0 (31.0)
Mean corpuscular volume, fL [1]	78 (70)	81 (75)
Reticulocytes	–	(0.5-1.0)
White blood cell, $\times 10^3/\text{mL}$ [2]	10.6 (6-17)	8.5 (5-15.5)
Platelets, $\times 10^3/\text{mL}$ [2]	(150-350)	(150-350)

Source: Adapted from [Hughes, 2018](#).

[1] Data are mean (-2 SD).

[2] Data are mean ((\pm 2 SD)).

RBC, red blood cell.

Table 3: Example Leukocyte Differential

Age	Total Leukocytes [1]	Neutrophils [2]		Lymphocytes		Monocytes		Eosinophils	
	Mean (Range)	Mean (Range)	%	Mean (Range)	%	Mean	%	Mean	%
1 year	11.4 (6-17.5)	3.5 (1.5-8.5)	31	7.0 (4-10.5)	61	0.6	5	0.3	3
2 years	10.6 (6-17)	3.5 (1.5-8.5)	33	6.3 (3-9.5)	59	0.5	5	0.3	3
4 years	9.1 (5.5-15.5)	3.8 (1.5-8.5)	42	4.5 (2-8)	50	0.5	5	0.3	3
6 years	8.5 (5-14.5)	4.3 (1.5-8)	51	3.5 (1.5-7)	42	0.4	5	0.2	3

Source: Adapted from [Hughes, 2018](#).

Ranges are estimates of 95% confidence limits and percentages refer to differential counts.

[1] Numbers of leukocytes are $\times 10^3/\mu\text{L}$.

[2] Neutrophils include band cells.

Table 4: Example Urinalysis Normal Findings

Urinalysis	Normal Finding
Appearance	Clear to cloudy
Bilirubin	Negative
Color	Almost colorless to amber
Glucose	Negative
Ketones	Negative
Nitrite	Negative
pH	4.5-8
Protein	Negative
Specific gravity	1.003-1.030
Urobilinogen	Normal

Source: Adapted from [Hughes, 2018](#).

REFERENCES

1 INTRODUCTION

In the event of a pandemic (eg, Coronavirus Disease 2019 [COVID-19] pandemic), epidemic, or other emergency not related to the study (eg, natural disaster, act of war or terrorism), restrictions may be issued at the country, state, regional, and/or local level that may affect study conduct, the scientific integrity of the study, or the safety and well-being of study participants and study site staff. When such restrictions and associated challenges (eg, site closures; travel restrictions; quarantines; pandemic- or epidemic-related illness in subjects, parents, caregivers, or study site personnel) prevent the conduct of study site visits (defined herein as a study visit that is conducted onsite at the study site, not remotely) or access to study product for an extended period, changes to certain study procedures will be implemented as described in this appendix and in accordance with regulatory requirements to ensure subject safety and continued treatment, care, and sponsor oversight.

Study sites must inform Aimmune (study sponsor) as soon as possible when such restrictions are issued or anticipated. Similarly, study sites must inform the sponsor when the restrictions are lifted. The resumption of study site visits will be determined in consideration of individual subjects; study sites; and local, state, regional, and national guidance as applicable; and in accordance with regulatory requirements.

The alternate procedures (also referred to as remote procedures) described in this appendix may be implemented for individual subjects; by study site; or at the local, state, regional, or national level as appropriate. As the ability to attend scheduled study site visits may change over time for individual subjects, study visits may alternate between remote procedures and study site visits as needed for flexibility until the restrictions are fully lifted and regular study site visits can resume. Additional details for the remote procedures will be provided in other supporting documents for study conduct. Procedures will be per protocol for subjects able to attend scheduled visits at the study site.

This appendix was prepared in consideration of the guidance released by the Food and Drug Administration (FDA Guidance on Conduct of Clinical Trials of Medical Products During COVID-19 Public Health Emergency updated 11 May 2020) and the European Medicines Agency (Guidance on the Management of Clinical Trials During the COVID-19 [Coronavirus] Pandemic version 3, 28 Apr 2020). As updates to these regulatory guidances are expected, the alternate procedures described in this appendix may be supplemented or superseded accordingly through supportive materials for study conduct as directed by the sponsor.

2 ENROLLMENT AND STUDY PROCEDURES

2.1 Recruitment, Screening, and Enrollment

The sponsor will notify study sites when recruitment, screening, and enrollment of subjects is suspended.

An exception to suspension of screening and enrollment is as follows: subjects who complete the first day of the screening double-blind, placebo-controlled food challenge (DBPCFC) before remote procedures are implemented may return to the study site to complete the second day of the DBPCFC per protocol and enroll in the study if eligible. However, continued participation in the study will be per investigator and parent/caregiver decision, based on the ability to attend study site visits and understanding the potential impact of the restrictions on study conduct.

The sponsor will notify study sites when recruitment, screening, and enrollment may resume. Rescreening may be considered for subjects who did not complete screening procedures, including those not starting screening food challenges, and for subjects who were enrolled in the study but did not start treatment due to the restrictions. Rescreening requires medical monitor approval and will be conducted per protocol.

2.2 Informed Consent

Study site personnel must obtain consent and assent (where required) before any remote procedures or rescreening procedures are conducted. Consent for remote procedures will include the release of contact information to allow the shipment of study product directly to the subject or designated responsible person's home or for study product to be picked up at the study site. Reconsent for other reasons (eg, protocol amendment, updated safety information) may be required during the restrictions.

The informed consent process (written; oral if the return of written consent for remote procedures is not possible) must be documented in the subject's source documents. Written consent is to be returned to the study site as soon as feasible for subjects who provided oral consent.

2.3 Duration of Study

The total duration of the study and duration of study treatment for individual subjects will be extended as needed to allow subjects to complete study treatment following delays due to the restrictions.

2.4 General Study Visit Procedures

Study visits will be conducted remotely (eg, telephone or video call) for subjects, parents, and caregivers who cannot attend scheduled visits at the study site due to the restrictions. Remote study visits will occur at the same intervals specified in the protocol schedules of activities.

On the day of a remote study visit, subjects will take their dose of study product at home per their usual dosing schedule.

During remote study visits, noninterventional visit procedures will be conducted according to the protocol schedules of activities as applicable and recorded in the subject's source documents:

- Adverse events review
- Concomitant medications review and instruction
- Treatment compliance/accountability review
- Diet/food allergen exposure review
- Food allergy instruction
- Asthma evaluation for subjects with asthma

Procedures that will not be completed during remote study visits are as follows:

- Weight, height, and vital signs measurements
- Questionnaires to assess atopic disease
 - Test for Respiratory and Asthma Control in Kids (TRACK)
 - Eczema Area and Severity Index (EASI)
- Physical examinations
 - Skin prick tests
 - Blood sample collection
- Food challenges
 - Food challenges will be delayed until the restrictions are lifted and regular study site visits resume. Food challenges are to be completed within 3 months after

regular study site visits resume for subjects who meet the protocol criteria for having a food challenge.

After completion of a remote study visit, study product will be dispensed as needed for dosing at home. Study site staff should confirm that study product was received by the appropriate individual.

After each remote study visit, site staff will contact the parent/caregiver by telephone within 3 days. In addition to the standard telephone call queries, receipt of study product will be confirmed (if applicable). The telephone call is at investigator discretion when study product is not dispensed after a remote study visit and dosing is continued at the same dose level.

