Adverse event or intercurrent illness	
Any intolerable adverse event that cannot be ameliorated using adequate medical intervention or that in the opinion of the investigator or sponsor may lead to undue risk if study treatment were continued, such as the following:
 
• Life-threatening symptoms (CoFAR grade 4), including anaphylaxis resulting in hypotension, neurologic compromise, or mechanical ventilation secondary to study treatment or food challenge.• Severe dose-related allergic hypersensitivity symptoms (CoFAR grade 3) that require intensive therapy (per investigator assessment, but may include interventions such as IV epinephrine, intubation, or admission to an intensive care unit) or are recurrent.• Poor control or persistent activation of secondary atopic disease (eg, atopic dermatitis, asthma).• Development of biopsy-documented eosinophilic esophagitis. 
Any adverse event that meets the early discontinuation criteria for study product tolerability or delays as follows:
 
• Tolerability of study product:
– Dose-limiting, moderate, or severe symptoms at any dose on initial dose-escalation day 1 or 2– Dose withheld for > 4 weeks for chronic or recurrent gastrointestinal adverse events at ≤ 20 mg/day– Unable to tolerate the 300 mg/day dose for 2 weeks within 40 weeks of up-dosing• Use of rescue medications:
– Treatment with epinephrine, beta-agonist, oxygen, IV fluids, > 2 doses of antihistamines, and/or glucocorticosteroids at any study product dose on initial dose-escalation day 1 or 2

Category Reason	Comment on Criteria

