9.4 Safety and Other Assessments

9.4.1 Assessments of Asthma Control

For subjects with asthma, the evaluation of asthma severity will be assessed using the classification in [Table 16](#).

Asthma control in subjects with pre-existing asthma will be assessed using scores from the Test for Respiratory and Asthma Control in Kids (TRACK) and by the incidence of asthma rescue medication use. The parent/caregiver is to complete the TRACK, a 5-item standardized questionnaire used to evaluate respiratory and asthma control in children aged < 5 years with symptoms consistent with asthma ([Zeiger, 2011](#)). Each item is scored on a 5-point scale from 0 (4 or more times a week) to 20 (not at all). Higher scores indicate better respiratory and asthma control.

Table 16: Evaluation of Asthma in Subjects Aged 0 to 4 Years Based on NHLBI Criteria

Classification	Intermittent (Step 1)	Persistent: Mild (Step 2)	Persistent: Moderate (Step 3 or 4)	Persistent: Severe (Step 5 or 6)
Symptoms	≤ 2 days/week	> 2 days/week but not daily	Daily	Throughout the day
Night-time awakenings	0	1-2 times/month	3-4 times/month	> 1 time/week
Short-acting inhaled beta2-agonist use	≤ 2 days/week	> 2 days/week but not daily	Daily	Several times per day
Interference with normal activity	None	Minor limitation	Some limitation	Extremely limited

Adapted from [NHLBI, 2007](#).

NHLBI, National Heart, Lung, and Blood Institute.

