2.6 Early Discontinuation

Subjects who discontinue early from the study while restrictions are in place will have a remote early discontinuation visit approximately 14 days after their last dose of study product. Noninterventional early discontinuation procedures will be conducted according to the protocol schedule of activities and as described in [Section 2.4](#). Parents/caregivers will be encouraged to bring subjects back to the study site to complete all early discontinuation procedures when regular study site visits resume, unless consent is withdrawn.

Subjects with unresolved adverse events at early discontinuation while restrictions are in place or who had gastrointestinal (GI) adverse events of interest will have safety follow-up ([Section 2.8](#)).

The criteria for early discontinuation due to missed doses while restrictions are in place will be based on the guidance provided later in this appendix ([Figure 1, Table 1](#)). Depending on the reason and number of missed doses, certain subjects who miss doses and stop study product dosing when the restrictions are in place will not be discontinued early from the study. Such subjects may reinitiate dosing after study site visits resume. When regular study site visits resume, the regular protocol criteria for early discontinuation due to missed doses will apply.

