2.8 Safety Follow-Up

In the event remote procedures are implemented, safety follow-up procedures will be conducted in accordance with the study protocol, except that subjects who discontinue due to GI adverse events will have remote study visits instead of study site visits when required, and no symptom-directed physical examinations will be performed.

Parents/caregivers of subjects who had GI adverse events of interest will be asked to complete the Pediatric Eosinophilic Esophagitis Symptom Scores version 2.0 (PEESS v2.0) per protocol.

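### Appendix 3 leaves the parent-completed TRACK out of remote visits without a stated reason, so some TRACK scores are avoidably missing during restrictions

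*Combined protocol and SAP*

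**What the plan says.** Appendix 3, Section 2.4 sets a general rule: "During remote study visits, noninterventional visit procedures will be conducted according to the protocol schedules of activities as applicable". It names what is kept, including the review of adverse events, the review of concomitant medications, and an asthma evaluation for children with asthma. A second list follows, introduced by "Procedures that will not be completed during remote study visits are as follows". Under its line on questionnaires for atopic disease stand the "Test for Respiratory and Asthma Control in Kids (TRACK)" and the EASI. No reason is given for either.

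Section 9.4.1 of the protocol describes the instrument: "The parent/caregiver is to complete the TRACK, a 5-item standardized questionnaire used to evaluate respiratory and asthma control in children aged < 5 years". It assesses control of pre-existing asthma by TRACK scores and by use of asthma rescue medication.

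Appendix 3, Section 2.6 covers children who stop early while restrictions are in place: "Noninterventional early discontinuation procedures will be conducted according to the protocol schedule of activities and as described in" Section 2.4. Parents are encouraged, but not required, to return later and complete the remaining procedures on site. Appendix 3, Section 2.8 keeps a different parent questionnaire going: "Parents/caregivers of subjects who had GI adverse events of interest will be asked to complete the Pediatric Eosinophilic Esophagitis Symptom Scores" (PEESS v2.0).

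Section 10.7 lists change from baseline in TRACK as an exploratory endpoint, and Section 10.6 provides summary statistics for TRACK with the safety data. Table 4 in Section 5.3 gives as one reason for stopping: "Poor control or persistent activation of secondary atopic disease (eg, atopic dermatitis, asthma)".

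**The concern.** TRACK and EASI are excluded together, but they differ in kind. Section 9.4.2 describes EASI as a scoring of clinical signs, which calls for someone to examine the child. TRACK calls only for a parent to answer five questions. Whatever justifies dropping EASI at a remote visit does not obviously justify dropping TRACK.

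At stake is the completeness of a listed endpoint that addresses a stated exploratory objective, change in control of pre-existing asthma (Section 2.3). Section 8.6.1.2 says that study product may worsen asthma, and Table 4 makes poor asthma control a ground for stopping. A child who stops for that reason during restrictions could be one whose TRACK score would have fallen. If that score is not taken, the missingness may depend on the outcome and possibly on the arm. Appendix 3, Section 5 offers no remedy for TRACK, because its alternative sensitivity analysis concerns the primary and secondary endpoints.

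**Working it through.** The plan gives no figure on this point to reproduce. The check is a comparison of text, followed by simple arithmetic for scale.

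**1. Does TRACK need the site?** Section 9.4.1 says "The parent/caregiver is to complete the TRACK, a 5-item standardized questionnaire". No examination, sample or equipment is involved. By the general rule of Appendix 3, Section 2.4 it would count as noninterventional, yet the next list in that section excludes it.

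**2. Could it be collected remotely under the same appendix?** Section 2.4 already provides a telephone or video contact at which the child's asthma is evaluated. Section 2.8 keeps PEESS v2.0. Section 3 has families return study diaries or send photographs of the pages. Remote collection of five more items is plausible on the appendix's own terms.

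**3. Where do scores go missing?**

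- *On treatment.* Sections 2.3, 2.4.2 and 2.4.3 of Appendix 3 extend treatment during restrictions, with remote visits at the usual intervals. Any TRACK due at such a visit is not taken.
- *At early discontinuation.* Section 2.6 imports the Section 2.4 exclusion. If TRACK is scheduled at that visit, it is missing unless the family returns. The visit grid of Appendix 5 could not be read in the text available, only its footnotes. Footnote 6 shows that TRACK belongs to the treatment-period schedule but does not say at which visits, so this part is conditional.
- *At exit.* Section 2.7 defers study exit until site visits resume. Exit TRACK for completers is postponed, not lost.

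**4. Scale.** Inputs: 132 planned subjects, 88 on AR101 and 44 on placebo, with 25% expected to drop out or discontinue early (Section 10.3). The share with asthma in this trial is not given. As an assumption I take 10% to 40%. The toddler study cited in Section 1.1 reports 27% with asthma or recurrent wheeze.

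Expected early discontinuations: 0.25 × 132 = 33.

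| Assumed asthma share | Eligible for TRACK (share × 132) | Eligible among the 33 discontinuations (share × 33) |
|---|---|---|
| 10% | 13.2, about 13 | 3.3, about 3 |
| 27% | 35.6, about 36 | 8.9, about 9 |
| 40% | 52.8, about 53 | 13.2, about 13 |

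The last column assumes that stopping is unrelated to asthma. Only children in that column who stop during restrictions and do not return would lose a discontinuation score, and the documents do not say how many that is. For sensitivity: at 27%, the AR101 arm has 0.27 × 88 = 23.8, about 24 eligible children, so each lost score is 1/24, about 4% of that group.

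**The case against.** The strongest reply is that little is lost. Use of asthma rescue medication is the other control measure in Section 9.4.1, and the medication review continues remotely. So do the adverse event review and the asthma evaluation, which by Table 16 covers symptom days, night awakenings, short-acting beta2-agonist use and activity limitation. A child stopped for poor asthma control is still recorded by adverse event and reason for stopping. All of this stands. A reader might infer that asthma-control data as a whole are lost; the documents do not support that. What is missing is the TRACK score. The retained data do not replace it, because Section 9.4.1 separates severity classification from control and Section 10.7 names change in TRACK.

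A reader might also infer that a late make-up score is worthless because it describes time off treatment. That is too strong: under Section 5.3 the ordinary early-discontinuation visit already falls about 14 days after the last dose, and the remote one does too. What remains is that a make-up visit is optional and comes after a further delay of unspecified length.

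A third tempting reading is that the surviving data are biased toward showing no harm, with, say, 2 to 4 of 24 AR101 scores (8% to 17%) selectively lost. The documents do not establish this. At 25% dropout about 0.25 × 24 = 6 of those children would stop at all, so 2 to 4 means that a third to two thirds of them stop during restrictions, fail to return, and do so because of asthma. Section 4.2 excludes moderate or severe persistent asthma and uncontrolled mild asthma, and Section 1.2.2 reports that adverse-event discontinuations in ARC003 were mostly gastrointestinal. Outcome-related missingness is possible, not shown.

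Finally, PEESS v2.0 is an imperfect comparator. It belongs to symptomatic periods and follow-up, where Section 5.5.1 already allows telephone contact, whereas TRACK is completed at the start of a visit. Appendix 3, Section 1 also leaves details of remote procedures to supporting documents. The first point weakens the analogy without making remote TRACK impractical. The second does not help, because Section 2.4 states an explicit exclusion and does not leave the matter open.

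**Conclusion.** The point holds as a minor, avoidable inconsistency. Appendix 3 excludes a short parent-completed form from remote visits, gives no reason, and extends the exclusion to remote early discontinuation, while keeping other noninterventional procedures, the asthma evaluation and PEESS v2.0. TRACK scores will be missing on treatment during restrictions, and possibly at discontinuation for children who do not return, provided that the schedule calls for TRACK at those visits.

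The missingness could be related to the outcome, since poor asthma control is a listed reason to stop. Its size cannot be determined from the documents: it depends on the share of children with asthma, on how many stop during restrictions, and on how many come back. The eligible group of about 13 to 53 children is an assumption-based range, not an estimate of loss. Primary and secondary efficacy analyses are untouched; only one exploratory endpoint and a descriptive safety summary are affected.

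**What to change.** In Appendix 3, Section 2.4, move TRACK from the list of procedures not completed to the list of procedures done remotely, by telephone, video or returned form. Apply this only at visits where the schedule already calls for TRACK, including remote early discontinuation if it is scheduled there; Section 2.6 then follows by its cross-reference. Record the mode of completion for each score. Leave EASI excluded.

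The cost is a one-line change to the appendix, a field for the mode of completion, and the parent's time for five items. The downside is that TRACK scores would come from mixed modes of completion; the recorded mode lets the analysis flag them. No clinical management rule changes.
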